**Table 2. Chemoradiation and Avelumab/Placebo Treatment Schedule**

	Lead-in Phase (7 days) a	CRT Phase (63 days)								Maintenance Phase b
	-- Day --	----- Day -----								
	1	1	8	15	22	25	29	36	39	43
IMRT (70 Gy/35 fractions/7 weeks; 1 fraction per day, 5 fractions/week [Monday – Friday])		X→	X→	X→	X	→	X→	X→	→	X→
Cisplatin (100 mg/m^2 Q3W)		X			X					X
Avelumab (10 mg/kg) or placebo	X		X		X c			X		Q2W

- Lead-in Phase to start 7 days prior to initiation of CRT Phase.
- Maintenance Phase to start after completion of the CRT Phase (ie, 2 weeks following completion of CRT) and be 12 months in duration. CRT phase may be extended as required for patient recovery from CRT; however, it is hypothesized that patients will receive maximal benefit from beginning maintenance as close to the scheduled time as possible.
- Day 25 dose of avelumab/placebo during the CRT Phase may be administered between Day 24 and Day 29. Cisplatin should be administered on a Monday or Tuesday if feasible to maximize overlap with IMRT. CRT = Chemoradiotherapy; IMRT = intensity-modulated radiation therapy; Q2W = every 2 weeks; Q3W = every 3 weeks.

The investigator will assess antitumor activity based on radiological assessments and clinical evaluation of patients using modified RECIST v1.1 at baseline, 12 weeks after the completion of CRT (ie, 10 weeks following completion of the CRT Phase of the study), every 16 weeks thereafter for 48 months (208 weeks), and every 24 weeks thereafter until confirmed disease progression per modified RECIST v1.1 and regardless of discontinuation of study treatment or initiation of subsequent anti-cancer therapy.

### 3. ENDPOINTS AND BASELINE VARIABLES: DEFINITIONS AND CONVENTIONS

#### 3.1. Primary Endpoint

- PFS per modified RECIST v1.1 by investigator assessment.

PFS is defined as the time from the date of randomization to the date of the first documentation of progressive disease (PD per modified RECIST v1.1) or death due to any cause, whichever occurs first.

#### 3.2. Secondary Endpoints

##### 3.2.1. Safety endpoints

- Adverse events (AEs) and laboratory abnormalities as graded by National Cancer Institute (NCI) Common Terminology Criteria for Adverse Events (CTCAE) v4.03.

AEs will be graded by the investigator according to CTCAE v4.03 and coded using the Medical Dictionary for Regulatory Activities (MedDRA).

- Vital signs (blood pressure, pulse rate).

### 3.2.2. Efficacy endpoints

- OS.

OS is defined as the time from the date of randomization to the date of death due to any cause.

- Antitumor activity: Pathologic complete response in any resected specimens, neck dissection.

Pathologic complete response is defined as the absence of histologically identifiable residual cancer in any resected specimen.

- Antitumor activity: Locoregional failure, objective response (OR), distant metastatic failure, and duration of response (DR), per modified RECIST v1.1 by investigator assessment.

OR is defined as complete response (CR) or partial response (PR) according to RECIST v1.1 from the date of randomization until the date of the first documentation of PD per modified RECIST v1.1 or death due to any cause. Response does not need to be confirmed at a subsequent assessment.

DR is defined, for patients with OR, as the time from the first documentation of objective response (CR or PR) to the date of first documentation of PD per modified RECIST v1.1 or death due to any cause.

Time to locoregional failure is defined as the time from the date of randomization to the date of the first documentation of locoregional PD per RECIST v1.1 with pathologic confirmation, locoregional clinically detectable progression with pathologic confirmation, salvage of primary tumor with tumor present on final pathology, salvage neck dissection >20 weeks after completion of CRT with tumor present on final pathology or death due to any cause, whichever occurs first.

Time to distant metastatic failure or distant metastasis is defined as the time from the date of randomization to the date of the first documentation of metastatic PD per RECIST v1.1 or death due to any cause, whichever occurs first.

### 3.2.3. Patient reported outcomes

- Disease-related symptoms and HRQoL as measured by the National Cancer Comprehensive Network (NCCN) Head and Neck Symptom Index-22 items (FHNSI-22), and the EuroQoL Group 5-Dimension 5- Level Self-Report Questionnaire (EQ-5D-5L).

The NCCN FHNSI-22 was developed using methods consistent with the Food and Drug Administration (FDA) PRO guidance (FDA, 2009) and surveyed input from patients with advanced cancers and physician experts (Cella D, et al., 2011). The FHNSI-22

questionnaire is specifically designed to be a stand-alone instrument to measure disease symptoms, treatment side effects and overall quality of life in patients with head and neck cancer.

Responses on the FHNSI-22 questionnaire are used to calculate a total score and scores for four subscales: TSE, DRS-P, DRS-E, and FWB. The questionnaire contains 22 items with 5-point Likert scales ranging from ‘not at all’ to ‘very much’. Higher scores mean better symptomatology, quality of life or functioning.

The EuroQol EQ-5D-5L is a patient-completed questionnaire designed to assess health status in terms of a single index value or utility score (Herdman M, et al., 2011). There are 2 components to the EuroQol EQ-5D-5L: a descriptive system in which individuals rate their level of problems (none, slight, moderate, severe, extreme/unable) in 5 areas (mobility, self-care, usual activities, pain/discomfort, and anxiety/depression) and a Visual Analogue Scale (VAS) in which patients rate their overall health status from 0 (worst imaginable) to 100 (best imaginable). Published weights are available that allow for the creation of a single summary score for the 5 Likert scale items.

### 3.2.4. Pharmacokinetic endpoints

- $C_{max}$  and  $C_{trough}$  for avelumab
- Area under the concentration-time curve extrapolated to infinity ( $AUC_{inf}$ ),  $C_{max}$ , clearance (CL), time to maximum plasma concentration ( $T_{max}$ ), elimination half-life ( $t_{1/2}$ ), and volume of distribution ( $V_z$ ) for cisplatin (total and free), as data permit.

**Table 3. PK Parameters to be Determined for Avelumab and Cisplatin**

Parameter	Definition	Method of Determination
$AUC_{inf}$	Area under the plasma concentration-time profile from time zero extrapolated to infinite time	$AUC_{last} + (C_{last}/k_{el})$ where $C_{last}$ is the predicted plasma concentration at the last quantifiable time point estimated from the log-linear regression analysis, and $k_{el}$ is the terminal phase rate constant calculated by linear regression of the log-linear concentration-time curve. Only those data points judged to describe the terminal log-linear decline will be used in the regression.
$C_{max}$	Maximum observed plasma concentration	Observed directly from data
$T_{max}$	Time for $C_{max}$	Observed directly from data as time of first occurrence
$t_{1/2}^a$	Terminal half-life	$\text{Log}_e(2)/k_{el}$ , where $k_{el}$ is the terminal phase rate constant calculated by a linear regression of the log-linear concentration-time curve. Only those data points judged to describe the terminal log-linear decline were used in the regression.

$C_{\text{trough}}$	Predose concentration during multiple dosing	Observed directly from data
CL	Clearance	Dose / $AUC_{\text{inf}}$
$V_z^a$	Apparent volume of distribution	Dose / ( $AUC_{\text{inf}} \cdot k_{\text{el}}$ )
$AUC_{\text{inf}}(\text{dn})^a$	Dose normalized $AUC_{\text{inf}}$	$AUC_{\text{inf}} / \text{Dose}$
$C_{\text{max}}(\text{dn})$	Dose normalized $C_{\text{max}}$	$C_{\text{max}} / \text{Dose}$

a If data permit

### 3.2.5. Immunogenicity endpoints

- ADA (neutralizing antibody) against avelumab  
 Anti-Drug Antibody (ADA) / Neutralizing antibodies (nAb) titers for avelumab.

### 3.2.6. Biomarker endpoints

- Tumor tissue biomarkers including but not limited to, PD-L1 expression and tumor-infiltrating CD8+ T-lymphocytes.

**Table 4. Biomarker Definition and Determination**

Parameter	Definition	Method of Determination
PD-L1	Protein expression using immunohistochemistry assay	VENTANA PD-L1 (SP263) Assay
Tumor infiltrating CD8+ lymphocytes	The number of CD8+ cells per unit area and the percent of counted cells that are scored as CD8+	Pathologist, assisted by image analysis

CCI [REDACTED]

[REDACTED]

[REDACTED]

[REDACTED]

### 3.4. Baseline Variables

#### 3.4.1. Study drug, study treatment and baseline definitions

In this study, ‘**study drug**’ refers to avelumab, avelumab-matching placebo, cisplatin or IMRT and ‘**study treatment**’ (or ‘**treatment arm**’) refers to one of the following:

- Arm A = Avelumab + SOC CRT;
- Arm B = Placebo + SOC CRT.

### **Start and end dates of study treatment:**

The date/time of first dose of study treatment is the earliest date/time of the first non-zero dose date/time for each of the study drugs.

The date/time of last dose of study treatment is the latest date/time of the last non-zero dose date/time for each of the study drugs.

### **Start dates of study treatment within each treatment phase:**

- Lead-in Phase

The start date/time of study treatment is the first dose date/time of avelumab or matching placebo across the Lead-in Phase visits.

- CRT Phase

The start date/time of study treatment is the earliest dose date/time of avelumab or matching placebo, cisplatin or IMRT across the CRT Phase visits.

- Maintenance Phase

The start date/time of study treatment is the earliest dose date/time of avelumab or matching placebo across the Maintenance Phase visits.

### **Definition of baseline:**

#### Definition of baseline for efficacy and PRO analyses

The last measurement prior to randomization will serve as the baseline measurement for efficacy and PRO analyses. If such a value is missing (since per protocol the first PRO assessment is planned to occur prior to dosing on Day 1 of the Lead-in Phase), the last measurement prior to the first dose of study treatment will be used as the baseline measurement except for analyses of tumor assessments data where the baseline assessment would be considered as missing.

#### Definition of baseline for immunogenicity analyses

The last available assessment prior to the start of treatment with avelumab is defined as 'baseline' result or 'baseline' assessment. If an assessment is planned to be performed prior to the first dose of avelumab in the protocol and the assessment is performed on the same day as the first dose of avelumab, it will be assumed that it was performed prior to avelumab administration, if assessment time point is not collected or is missing.

#### Definition of baseline for safety analyses

The last available assessment prior to the start of study treatment is defined as 'baseline' value or 'baseline' assessment for safety analyses. If an assessment is planned to be performed prior to the first dose of study treatment in the protocol and the assessment is performed on the same day as the first dose of study treatment, it will be assumed that it was

performed prior to study treatment administration, if assessment time point is not collected or is missing. If assessment time points are collected, the observed time point will be used to determine pre-dose on study day 1 for baseline calculation. Unscheduled assessments will be used in the determination of baseline. However, if time is missing, an unscheduled assessment on study day 1 will be considered to have been obtained after study treatment administration.

Patients who start treatment and discontinue from the study on the same day may have two different sets of data collected on study day 1 (one during study and one in the End of Treatment (EOT) visit). Data reported at the EOT visit are not eligible for baseline selection.

If a scheduled pre-dose measurement actually occurred post-dose, then the corresponding measurement will be treated and analyzed similar to an unscheduled post-dose measurement.

Baseline for RR and QT/QTc interval assessments will be derived from the visit where both RR and QT are not missing. Triplicate ECGs are collected in the study for approximately 30 patients in each treatment arm and the baseline for each ECG measurement is the average of the pre-dose replicate measurements on the baseline day. Unscheduled assessments will not be included in the calculation of the average. QTcB and QTcF will be derived based on RR and QT. The average of the replicate measurements will be determined after the derivation of the individual parameter at each time point.

#### Definition of baseline for biomarker analyses

Baseline biomarker is the last biomarker assessment prior to the start of study treatment. If an assessment is planned to be performed prior to the first dose of study treatment in the protocol and the assessment is performed on the same day as the first dose of study treatment, it will be assumed that it was performed prior to study treatment administration, unless otherwise defined in the protocol.

#### **3.4.2. Baseline Characteristics**

Randomization is stratified by the following, as recorded in the Interactive Response Technology (IRT):

- Tumor (T) stage (<T4 vs T4);
- Nodal (N) stage (N0/N1/N2a/N2b vs N2c/N3);
- HPV status (positive vs negative) as measured by p16 expression by IHC.

The primary analyses of PFS and OS will be stratified by these randomization stratification factors.

Other baseline characteristics (including demographics, physical measurements, and disease history) are described in Section 6.5.1. These baseline characteristics are not planned to be included as stratification variables or covariates in statistical models unless otherwise specified in Section 6.

### 3.5. Safety Endpoints

#### 3.5.1. Adverse events

##### Treatment-Emergent Adverse Events

Treatment-emergent adverse events (TEAEs) are those events with onset dates occurring during the on-treatment period.

**On-treatment period** is defined as the time from the first dose of study treatment through minimum (30 days + last dose of study treatment, start day of new anti-cancer drug therapy – 1 day). The start day of new anti-cancer drug therapy after the first dose of study treatment is derived as outlined in Section 5.2.5.

##### Adverse Events of Special Interest (AESIs)

AESIs are immune-related adverse events (irAE) and infusion-related reactions (IRRs). The criteria for classification of an AE as an irAE or IRR are described in Appendix 1 and Appendix 2, respectively.

##### 3-Tier Adverse Events

It should be recognized that most studies are not designed to reliably demonstrate a causal relationship between the use of a pharmaceutical product and an adverse event or a group of adverse events. Except for select events in unique situations, studies do not employ formal adjudication procedures for the purpose of event classification. As such, safety analyses are generally considered as an exploratory analysis and its purpose is to generate hypotheses for further investigation. The 3-tier approach facilitates these exploratory analyses.

Adverse events and clusters of adverse events, of any causality and treatment-related, will also be summarized following a 3-tier approach. Under this approach, AEs are classified into 1 of 3 tiers.

Tier-1 events: These are pre-specified events or clusters of events of clinical importance and will be described in the Safety Review Plan (SRP).

Tier-2 events: These are events that are not Tier-1 but are “common”. A MedDRA PT is defined as a Tier-2 event if it is reported by

- a) at least 10% of patients with any grade in any treatment arm, or
- b) at least 5% of patients with Grade 3, 4 or 5 in any treatment arm.

Tier-3 events: All other AEs that are classified neither as Tier-1 nor Tier-2.

#### 4. ANALYSIS SETS

Data for all patients will be assessed to determine if patients meet the criteria for inclusion in each analysis population prior to releasing the database and classifications will be documented per Pfizer’s standard operating procedures.

Only patients who signed informed consent will be included in the analysis sets below.

Table 5 summarizes the use of the analysis sets for efficacy, safety, baseline characteristics and exposure.

**Table 5. Statistical Analyses by Analysis Set**

Endpoints	Full Analysis Set	Per Protocol Analysis Set	Safety Analysis Set
Baseline Characteristics	✓		✓
Prior and Concomitant Therapies	✓		✓
Exposure			✓
Efficacy: Primary	✓	✓	
Efficacy: Secondary	✓	✓ (OS only)	
CCI			
Safety			✓

##### 4.1. Full Analysis Set

The full analysis set (FAS) will include all randomized patients. Patients will be classified according to the study treatment assigned at randomization.

##### 4.2. Safety Analysis Set

The safety analysis set will include all patients who receive at least one dose of study drug. Patients will be classified according to the study treatment assigned at randomization unless the incorrect treatment(s) was/were received throughout the dosing period in which case patients will be classified according to the first study treatment received.

##### 4.3. Other Analysis Set

###### 4.3.1. Per-protocol analysis set

Per protocol (PP) analysis set is a subset of the FAS and will include patients who do not meet any of the following criteria that could impact the key objectives of the study. Patients who meet any of the following criteria will be excluded from the PP analysis set.

- Patient did not receive at least one dose of the randomized study treatment;
- Baseline ECOG status  $\geq 2$ ;

- Patient did not meet inclusion criterion 5 or met any of exclusion criteria 1, 13 or 17; namely patient received any anti-cancer therapy for advanced stage SCCHN or immunotherapy with an anti-PD-1, anti-PD-L1, anti-PD-L2, anti-CD137, or anti-CTLA-4 antibody (including ipilimumab), or any other antibody or drug specifically targeting T cell co-stimulation or immune checkpoint pathways prior to randomization or patient received other non-protocol active anticancer therapy within 4 weeks prior to randomization.

The list of patients who are excluded from the PP analysis set will be documented with the reason for exclusion.

#### **4.3.2. PK analysis sets**

The PK concentration analysis set is a subset of the safety analysis set and will include patients who have at least one post-dose concentration measurement above the lower limit of quantitation (LLQ) for avelumab or cisplatin (total and free).

The PK parameter analysis set is a subset of the safety analysis set and will include patients who have at least one of the PK parameters of interest for avelumab or cisplatin (total and free).

#### **4.3.3. Biomarker analysis set**

The biomarker analysis set is a subset of the safety analysis set and will include patients who have at least one screening biomarker assessment. For the optional tumor biopsy assessment, a second analysis set will include patients who have at least one dose of avelumab and who have at least one on-treatment biomarker assessment. Analysis sets will be defined separately for blood-based and tumor tissue-based biomarkers.

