### 3. STUDY DESIGN

#### 3.1. Overall Study Design

This is a Phase 3, international, multicenter, randomized, double-blind, parallel, 2-arm study in patients with previously untreated, histologically confirmed locally advanced SCCHN (oral cavity, oropharynx, larynx, or hypopharynx) who are candidates for definitive CRT with cisplatin.

The study is designed with the primary objective of demonstrating that treatment with avelumab in combination with SOC CRT is superior to SOC CRT alone in prolonging PFS.

[figure not shown]
One interim analysis for the assessment of PFS will be conducted to allow early stopping of the study for futility or to demonstrate early superiority of avelumab in combination with SOC CRT compared to SOC CRT alone, and to assess the safety of avelumab in combination with SOC CRT.

A total of approximately 640 patients will be randomized in a 1:1 ratio to either Arm A (avelumab + SOC CRT) or Arm B (placebo + SOC CRT). Randomization will be stratified by tumor (T) stage (<T4 vs T4), nodal (N) stage (N0/N1/N2a/N2b vs N2c/N3), and HPV status (positive vs negative) as measured by p16 expression by IHC.

The study schematic is provided in [Figure 3](#).

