**Figure 3 Study Design**

- a. Patients with LA SCCHN (oral cavity, oropharynx, larynx, or hypopharynx) eligible for front-line treatment: HPV negative disease stage III, IVa, IVb; non-oropharyngeal HPV positive disease stage III, IVa, IVb; HPV positive oropharyngeal disease T4 OR N2cOR N3 (staging per TNM [tumor, node, metastases] guidelines for head and neck sites AJCC 7th Edition). (Note: entry criteria for patients with HPV-positive tumors are different than for HPV-negative tumors).
- b. Avelumab or placebo IV to be administered on Day 1 of the Lead-in Phase (1 week prior to the start of the CRT Phase), and on Days 8, 25, and 39 during the CRT Phase.
- c. SOC CRT = IMRT (70 Gy/35 fractions/7weeks; 1 fraction/day, 5 fractions/week) for 7 weeks + cisplatin (100 mg/m^2 Days 1, 22, 43) during the CRT Phase.
- d. Maintenance Phase to start after completion of the CRT Phase and continue for 12 months.
- e. Patients will continue treatment until confirmed disease progression as assessed by Investigator per modified RECIST v1.1.

AJCC = American Joint Committee on Cancer; CRT = chemoradiotherapy; HPV = human papillomavirus; IMRT = intensity-modulated radiation therapy; LA = locally advanced; Q2W = every 2 weeks; RECIST = Response Evaluation Criteria in Solid Tumors; SCCHN = squamous cell carcinoma of the head and neck; SOC = standard of care.

There will be 3 treatment phases in this study.

- **Lead-in Phase:** On Day 1 of the Lead-in Phase of the study, patients will receive a single dose of avelumab or matching placebo, administered 7 days prior to initiation of the CRT Phase;
- **CRT Phase:** Avelumab or matching placebo will be administered on Days 8, 25, and 39 in conjunction with SOC CRT starting on Day 1 of the CRT Phase;
- **Maintenance Phase:** Following completion of the CRT Phase, avelumab or matching placebo will be administered Q2W for 12 months during the Maintenance Phase.

The treatment schedule is described in the following table.

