### **6.2.1. Tumor Biospecimens**

#### **6.2.1.1. Mandatory Tumor Tissue**

An archival FFPE tumor tissue block from the most recent tumor resection or biopsy must be provided for all patients enrolled in the study and submitted to the Central Laboratory prior to randomization. If an FFPE tissue block cannot be provided, 15 unstained slides (10 minimum) will be acceptable. Tumor tissue from cytologic sampling (eg, fine-needle aspiration, including FFPE cell pellet material), is not adequate and should not be submitted.

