#### **6.2.1.2. Optional Tumor Tissue – Lead-In Phase**

An optional tumor biopsy, to be collected 4 to 7 days following the single dose of avelumab in the Lead-in Phase, is requested for analysis of potential biomarkers of response. The de novo biopsy should be FFPE as per routine (see Study Manual), and the resulting FFPE tissue block(s) should be submitted to the Central Laboratory.

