#### **6.2.6. Biomarker endpoints**

There are two sets of biomarkers, those collected at screening (pre-treatment tumor sample), and the optional tumor sample after one dose of avelumab. The optional tumor samples will be analyzed separately.

Summary statistics for pre-treatment biomarkers will be presented by treatment arm and overall. Summary statistics for on-treatment biomarkers will additionally include the ratio to baseline for continuous biomarkers, and a contingency table for non-continuous biomarkers, as appropriate.

Continuous biomarkers will be split at the median ( $<$  and  $\geq$  median), and will be included as a covariate in an exploratory Kaplan-Meier analysis for PFS, as described in Section 6.1.1.1; no other covariates will be included. Non-continuous biomarkers will either be split at an appropriate point in their distribution, and classified as above and below the split (0,1), or the actual categories will be included in the survival analysis.

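### Read literally, SAP 4.3.3 keeps Arm B out of the optional on-treatment biopsy analysis, so change from an archival baseline would have no concurrent control

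*SAP*

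**What the plan says.** The SAP defines two biomarker sets in section 4.3.3. The first needs a screening biomarker assessment and covers both arms. For the optional biopsy, "a second analysis set will include patients who have at least one dose of avelumab and who have at least one on-treatment biomarker assessment". Matching placebo is not named. SAP 6.2.6 describes the two groups of markers as "those collected at screening (pre-treatment tumor sample), and the optional tumor sample after one dose of avelumab", and says that the optional samples are analyzed separately.

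On reporting, SAP 6.2.6 states "Summary statistics for pre-treatment biomarkers will be presented by treatment arm and overall". It then adds "Summary statistics for on-treatment biomarkers will additionally include the ratio to baseline for continuous biomarkers", with a contingency table for markers that are not continuous.

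On the samples, Protocol 6.2.1.1 requires of everyone: "An archival FFPE tumor tissue block from the most recent tumor resection or biopsy must be provided for all patients". Protocol 6.2.1.2 describes the later sample as "An optional tumor biopsy, to be collected 4 to 7 days following the single dose of avelumab in the Lead-in Phase".

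On the design, Protocol 3.1 reads "This is a Phase 3, international, multicenter, randomized, double-blind, parallel, 2-arm study in patients", and in the Lead-in Phase "patients will receive a single dose of avelumab or matching placebo, administered 7 days prior to initiation of the CRT Phase". Allocation is 1:1. The optional biopsy is one row of the Schedule of Activities (Protocol Table 2, footnote 23), which is the same for both arms.

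**The concern.** Sites do not know who received avelumab, so they cannot offer the optional biopsy to avelumab patients only. If Arm B patients are biopsied as well, the trial holds a randomized, blinded control for the effect of one dose on PD-L1 and CD8. An inclusion rule that requires a dose of avelumab sets that control aside.

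The planned measure for continuous markers is a within-patient ratio. Its denominator comes from an archival block, which under the inclusion criteria may be from the primary tumor or a node. Its numerator comes from a fresh biopsy taken days after dosing, and the text that describes that biopsy does not require the same site. Differences in tissue handling, site and sampling therefore enter the ratio together with any drug effect.

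The secondary objective in Protocol 2.1 concerns predictive biomarkers of sensitivity or insensitivity. In Arm A alone, an association between a post-dose marker and PFS could equally be prognostic. At stake is the interpretation of this one analysis.

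**Working it through.** The plan gives no sample size, uptake or effect size for the optional biopsy, so there is no figure to reproduce. The check is a reading of the text, followed by illustrative arithmetic.

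**Step 1: does the wording exclude Arm B?**

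- SAP 4.3.3 requires a dose of avelumab. Arm B receives placebo with chemoradiotherapy, so no correctly treated Arm B patient qualifies.
- SAP 3.4.1 defines study drug by listing avelumab and its matching placebo as separate items. The SAP therefore had a term that covers both.
- The sentence that extends avelumab to matching placebo is in SAP 6.5.3.1 and applies to what follows there. No such sentence governs 4.3.3 or 6.2.6.
- Protocol 9.2.6 defines the biomarker set by a screening assessment and does not require avelumab.

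**Step 2: is 6.2.6 consistent with this?** If on-treatment summaries are by arm, as the word *additionally* suggests, an Arm B column is needed, and the literal 4.3.3 set would leave it empty. If they are not by arm, there is no control. Either way the text needs a change.

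**Step 3: how many biopsies are involved?** Assume an uptake u that is equal in both arms, with 640 patients randomized 1:1.

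Arm B biopsies outside the set = 640 × u × 1/2

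- u = 5%: 32 biopsies, 16 outside the set
- u = 10%: 64 biopsies, 32 outside
- u = 20%: 128 biopsies, 64 outside
- u = 40%: 256 biopsies, 128 outside

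The share is one half at any uptake.

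**Step 4: what does the missing control do to the ratio?** Let d be the true multiplicative effect of avelumab. Let s be the non-drug shift between archival and fresh samples, taken as equal in both arms, which randomization and the blind make reasonable.

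- Arm A ratio to baseline = s × d
- Arm B ratio to baseline = s
- Arm A ÷ Arm B = d

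| Assumed s | Arm A ratio if d = 1 | Arm A ratio if d = 1.5 | Arm A ÷ Arm B |
|---|---|---|---|
| 0.80 | 0.80 | 1.20 | 1.0 or 1.5 |
| 1.00 | 1.00 | 1.50 | 1.0 or 1.5 |
| 1.25 | 1.25 | 1.875 | 1.0 or 1.5 |
| 1.50 | 1.50 | 2.25 | 1.0 or 1.5 |

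An Arm A ratio of 1.50 arises with no shift and a true effect of 1.5, and equally with a shift of 1.5 and no effect. The Arm A data alone cannot tell these apart; the between-arm ratio can. The values of s and d are assumptions that show the mechanism. They are not estimates.

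**Step 5: timing.** Lead-in Day 1 is 7 days before CRT Day 1, so a biopsy on day 7 falls on CRT Day 1. Protocol section 6 allows assessments before or after the daily IMRT fraction, so a day-7 sample could follow the first fraction.

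**The case against.** The strongest reply is that this is loose wording and not a decision. The safety sections tabulate events leading to discontinuation of avelumab by treatment arm (SAP 6.6.1.1) and give a between-arm risk difference for infusion reactions associated with avelumab (SAP 6.6.4). Those tables make sense only if the word covers placebo. The protocol's description of the biopsy uses avelumab in the same way. When the SAP means Arm A only it can say so, as the next section, 4.3.4, does. SAP 5.2 also makes by-arm reporting the general default, although it refers to a table that does not visibly list the biomarker set. All this stands as evidence that both arms may have been intended. It does not remove the problem, because 4.3.3 is an inclusion rule that a programmer would apply as written.

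A second reply is that the objective itself speaks of samples after one dose of avelumab, that the analysis is descriptive and exploratory, and that nothing says the ratio will be attributed to the drug. This limits the importance of the point. But the objective names predictive biomarkers, and Protocol 7.5.1 wants the paired samples to show how the tumor changed over therapy. Both call for a control.

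A reader might infer more than the documents support:

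- *Arm B samples are thrown away.* Nothing says that they are destroyed, left unassayed or omitted from listings.
- *Patients with a zero baseline are dropped.* A ratio is undefined at zero, but no rule removes such patients, and a categorized marker would show conversion in the contingency table.
- *A day-7 sample may follow cisplatin.* Table 2 footnote 1 and Protocol section 6 place assessments before IV study treatment unless otherwise indicated, which largely covers this. A same-day IMRT fraction is the remaining possibility.

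Some biomarker text is redacted, so a comparison planned there cannot be ruled out.

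**Conclusion.** The point holds in a limited form. As written, SAP 4.3.3 either excludes the concurrent control from the on-treatment biopsy analysis or conflicts with by-arm reporting in SAP 6.2.6. Under the literal reading, change in PD-L1 or CD8 cannot be attributed to avelumab, and predictive value cannot be distinguished from prognostic value.

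This rests on three assumptions: that Arm B patients are biopsied, which is inferred from the blind and the common schedule and not stated; that uptake is similar in the two arms, for the one-half share; and that the non-drug shift is common to both arms, for the between-arm ratio to recover the drug effect.

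It would be tempting to conclude that the planned estimate is biased by a particular amount, such as 25%. The documents give no shift, so its size and direction are unknown and it may be negligible. Restoring Arm B is also necessary rather than sufficient for a predictive claim: the marker is measured after randomization, and only in patients who agreed to a second biopsy. The effect is confined to this secondary biomarker analysis. PFS, OS and safety inference are unaffected.

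**What to change.** In SAP 4.3.3, change the dosing criterion for the optional-biopsy set to at least one dose of *avelumab or matching placebo*. In SAP 6.2.6, state that on-treatment biomarkers are summarized by treatment arm and that change from baseline is compared between Arm A and Arm B.

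Two optional additions: for markers that can be zero at baseline, use a scale that tolerates zero, such as percentage-point change or the logarithm after adding a fixed constant; and flag samples taken after the first IMRT fraction.

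The cost is a SAP wording change and an extra table column. No new patients or biopsies are needed. The one possible expense is assaying Arm B blocks that would otherwise go unread. If the sponsor does intend an Arm A-only set, SAP 4.3.3 should say so, and 6.2.6 should state that the ratio to baseline is descriptive and not attributable to avelumab.
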